|------------------------|-----------|
| 4.2.2 Study Team | 25 |
| 4.2.3 Adverse Events | 25 |
| 4.2.4 Study Procedures | 26 |
| 4.2.5 Data Quality | 27 |
| 4.3 Privacy | 27 |
| 5 Dissemination | 28 |
| 5.1 Data Sharing Plan | 28 |
| 5.2 Access to Data | 29 |

1. Synopsis

| | |
|---|---|
| Title: | Goal-setting in a standalone, digital weight loss intervention: a pilot factorial trial |
| Grant Number: | P30DK116074 |
| Study Description: | This pilot optimization trial examines the impact of easier versus harder goals across 4 goal domains--calories, steps, eating window, Red Zone Foods--in a 10-week digital weight loss intervention for adults with overweight or obesity. |
| Objectives: | The purpose of the study is to evaluate the feasibility and acceptability of these goals. |
| Endpoints: | The behavioral intervention is 10 weeks in length and will not be terminated early based on efficacy. The study is expected to end after our target sample size is reached and the final participant has completed the intervention. |
| Study Population: | The study population will consist of adults (ages 18+) with body mass index (BMI) 25.0 to 45.0 kg/m ² from a national sample of the general population. |
| Phase or Stage: | Multiphase Optimization Strategy: Preparation Phase |
| Description of Sites/Facilities Enrolling Participants: | All study procedures, including recruitment, intervention delivery, and assessment, will take place remotely. |
| Description of Study Intervention/Experimental Manipulation: | All participants (N=32) receive a 10-week behavioral weight loss intervention that includes the following empirically-supported components: a weight loss goal of 5%, which is consistent with obesity treatment guidelines; daily self-monitoring of body weight, calories, steps, and eating window; daily to weekly self-monitoring of Red Zone Foods; weekly tailored feedback via email; and weekly behavioral lessons and action plans via email. Participants are randomized to 1 of 16 conditions that vary in receipt of easier versus harder goals across 4 different goal domains: calorie goal, step goal, eating window goal, and Red Zone Foods goal. |
| Study Duration: | The intervention will last 10 weeks. |
| Participant Duration: | Individual participants will complete study related tasks within 3 months after randomization. |

2. Purpose, Background and Rationale

2.1 Objective

The overall goal is to examine the feasibility and acceptability of easier versus harder goals. If feasibility and acceptability are established, efficacy can be evaluated in a subsequent, fully-powered optimization trial. The overarching research question of this line of work is to determine the optimal goal setting intensities that maximize weight loss in a digital intervention for adults with overweight or obesity.

2.2 Aim

Aim 1. To evaluate the feasibility of the four types of goals and the other intervention components.

Aim 2. To determine the acceptability of the four types of goals and the other intervention components.

2.3 Background and Significance

2.3.1 Obesity

Obesity is a significant public health problem. Obesity has become a pervasive health concern in the United States, with rates of 42% among adults and another 30+% overweight. Excess weight heightens risk for chronic diseases, including type 2 diabetes, and can magnify psychological distress as a result of weight stigma. Behavioral weight loss interventions that involve frequent in-person meetings, diet and exercise goals, and behavioral strategies are the gold standard for treating overweight and obesity. These

traditional treatments are effective in producing weight loss up to 10%, but often lack scalability. This research is significant because it will optimize a behavioral weight loss intervention that has potential for broad reach and scalability.

2.3.2 Fully digital weight loss interventions

Digital health interventions that deliver treatment remotely seek to minimize burden and decrease costs compared to in-person interventions. With widespread penetration of smartphones among U.S. adults, digital health interventions have potential to reach broad geographic segments of the population. Compared to traditional interventions with counseling, *standalone* digital interventions offer greater scalability given lower personnel costs, and produce modest weight loss. However, weight loss tends to be modest; thus, more work is needed to enhance the efficacy of fully digital approaches.

2.3.3 Goal setting

Goal setting is a core component of behavioral obesity treatment. Goals can focus on behaviors (e.g., to exercise more) or outcomes (e.g., to lose weight). Many behavioral obesity treatments include goals for weight loss, physical activity, and calories, yet there is large variability in the specific intensities of these goals. Past research has shown that personalized goals are helpful at promoting behavior change, adaptive goals help more than static goals, immediate goals help more than gradual goals, and larger goals help more than smaller goals. However, to our knowledge, no study has examined the optimal goal intensity (i.e., harder versus easier goals) to be given in a fully digital weight loss intervention. Doing so would aid in identifying the most efficacious and least burdensome approach to goal setting in a highly scalable context.

2.4 Theoretical Framework

Self-regulation theories, including Social Cognitive Theory and Control Theory, posit that behavior change occurs through comparison of one's behavior to one's goals or past performance. Meta-analyses have demonstrated that goal setting, self-monitoring, and feedback work in tandem to promote greater behavior change and weight loss.

2.5 Using the Multiphase Optimization Strategy (MOST)

[figure not shown]
The Multiphase Optimization Strategy (MOST) is an engineering-inspired framework used for systematically constructing multicomponent behavioral interventions. MOST involves three phases: Preparation, Optimization, and Evaluation. In the Preparation phase, components and their respective levels of interest are identified and pilot tested. A conceptual model is created to depict how behavior change occurs through the various components and mechanisms. In the Optimization phase, the unique and combined effects of those components are evaluated in a fully-powered trial. Often, a factorial design is used. Components and component-levels that produce a minimal clinically important difference are retained in the newly optimized intervention, whereas those that produce minimal or iatrogenic effects are removed. Lastly, in the Evaluation phase, the newly optimized intervention is tested against a meaningful comparator to determine efficacy of the intervention package. The goal is to achieve intervention EASE, by balancing the Effectiveness of the intervention against other constraints such as Affordability, Scalability, and Efficiency.

2.6 Advancing Knowledge in the Field

No study, to our knowledge, has examined the optimal goal setting intensity in a fully digital weight loss intervention. Examining both the unique and combined effects of different goal intensities will enable creation of an intervention that maximizes weight loss while minimizing undue patient burden and effort.

3. Research Plan and Design

The study aim is to conduct a 10-week pilot optimization trial (N=32) using a factorial design to evaluate goal setting intensities (easier vs. harder) across 4 goal domains: calorie goal, step goal, eating window goal, and Red Zone Food goal in a fully digital weight loss intervention for adults with overweight/obesity. As shown in the conceptual model (**Figure**), participants will receive either an easier or harder version of 4 goals, and we will examine their effect on perceived helpfulness, perceived ease, goal attainment, self-monitoring engagement, and subsequently, diet and physical activity, and weight loss.

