3.2 Study Design

This optimization trial will use a 2^4 full factorial design (i.e., $2 \times 2 \times 2 \times 4$) to test easier vs. harder versions of 4 goals. As shown in the **Table**, for each goal domain, half of participants will be randomly assigned to receive the easier version while the other half will receive the harder version. In total, participants will be randomized to 1 of 16 experimental conditions. A factorial trial compares means across *combinations* of conditions in order to test main effects of components and their interactions. For example, the main effect of calorie goal intensity is the mean for the participants who receive the easier version of it (i.e., experimental conditions 1-8) versus the mean of those who receive the harder version of it (i.e., conditions 9-16).

| Experimental Condition | Core | Calorie Goal | Step Goal | Eating Window Goal | Red Zone Food Goal |
|------------------------|------|--------------|-----------|--------------------|--------------------|
| 1 A | Yes | Easier | Easier | Easier | Easier |
| 2 B | Yes | Easier | Easier | Easier | Harder |
| 3 C | Yes | Easier | Easier | Harder | Easier |
| 4 D | Yes | Easier | Easier | Harder | Harder |
| 5 E | Yes | Easier | Harder | Easier | Easier |
| 6 F | Yes | Easier | Harder | Easier | Harder |
| 7 G | Yes | Easier | Harder | Harder | Easier |
| 8 H | Yes | Easier | Harder | Harder | Harder |
| 9 I | Yes | Harder | Easier | Easier | Easier |
| 10 J | Yes | Harder | Easier | Easier | Harder |
| 11 K | Yes | Harder | Easier | Harder | Easier |
| 12 L | Yes | Harder | Easier | Harder | Harder |
| 13 M | Yes | Harder | Harder | Easier | Easier |
| 14 N | Yes | Harder | Harder | Easier | Harder |
| 15 O | Yes | Harder | Harder | Harder | Easier |
| 16 P | Yes | Harder | Harder | Harder | Harder |

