3.7.1 Randomization and Masking

Following recommendations for factorial designs, we will randomize participants to the 16 conditions using permuted block randomization with a block size of 16. The

allocation sequence will be generated by the study's PI and stored in REDCap. Study staff will use REDCap to implement the random allocation sequence (i.e., randomize a participant) once both the baseline weight and web-based surveys are submitted. The first day of the weight loss intervention will occur approximately two days after randomization. On that day, participants will receive an automated email describing their treatment assignment. Participants will not be masked to treatment assignment. Study staff will not be masked to treatment assignment due to logistical limitations and the need for quality assurance. However, all surveys will be sent via REDCap and completed without study staff involvement. In addition, study staff will not have access to the allocation sequence.

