3.8 Sample Size and Statistical Power

Aligning with recommendations for conducting pilot studies, the purpose of our proposed pilot study is to assess feasibility and acceptability of the intervention. As a result, no power analysis will be conducted. The sample size (n=32) was selected to have the same number of participants (n=2) per condition and allows us to meet budget and time restrictions.

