3.9 Statistical Analysis

We will use descriptive data to assess feasibility and acceptability outcomes, and will compare them to our *a priori* feasibility benchmarks, outlined in the **Table** above. To evaluate exploratory changes in efficacy outcomes that will be evaluated in a larger-scale trial, we will descriptively assess the main effects of each goal-setting component being tested, along with their interactions. Unlike in an RCT that compares the means of each treatment arm to one another, a factorial trial compares the means across *combinations of experimental conditions* and uses the entire sample, which makes it an efficient and economical study design. For example, the main effect of the Calorie Goal intensity is calculated by computing the mean for the participants who receive the harder goal (i.e., those in experimental conditions 9-16 in the Table above) versus the mean of those who

receive the easier goal (i.e., those in experimental conditions 1-8), collapsed across the other factors. In a subsequent optimization trial, we will be powered to detect these effects.

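### Whole-person primary outcomes have no stated breakdown by assigned goal intensity: extend the main-effect summaries to them and add one exploratory table by number of harder goals

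*Combined protocol and SAP*

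**What the plan says.** - **Rationale.** Section 2.6: "Examining both the unique and combined effects of different goal intensities will enable creation of an intervention". The same sentence adds the aim of limiting burden on patients. Section 2.1 makes feasibility and acceptability of easier versus harder goals the question for this pilot, and makes the powered trial depend on the answer. Section 3.6.1 says that the primary outcomes concern the goals and how intense they are.
- **Design.** Section 3.2: "In total, participants will be randomized to 1 of 16 experimental conditions". For each goal, "half of participants will be randomly assigned to receive the easier version while the other half will receive the harder version". Section 3.2 describes comparing means over combinations of conditions "in order to test main effects of components and their interactions". Section 3.7.1 specifies "permuted block randomization with a block size of 16". Section 3.8: "The sample size (n=32) was selected to have the same number of participants (n=2) per condition".
- **Primary rows.** Among the unstarred rows of table 3.6.2 are tracking of weight, steps and diet (75% each), 10-week retention (80%), 10-week survey completion (80%) and recommending the program (80%).
- **Analysis.** Section 3.9 has two parts. Feasibility and acceptability are described and set against the benchmarks. Then, for exploratory efficacy outcomes, "we will descriptively assess the main effects of each goal-setting component being tested, along with their interactions". No breakdown by goal level, or by number of harder goals, is attached to the first part.

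**The concern.** Six of the primary results describe how a person copes with the whole package, not with one goal. If harder goals are burdensome, this is where it would show. Section 3.9 states only a comparison with the benchmark for these rows, which can be read as one pooled percentage over all 32 people.

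A pooled percentage averages over people given anything from no harder goals to four. It can meet 80% while those with three or four fall well short. Five of the 16 conditions carry three or four harder goals and would presumably go forward to the powered trial. The pilot would then support going ahead without having looked, as a planned matter, at whether those packages are tolerated or whether dropout is likely to differ by assignment.

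**Working it through.** **Inputs.** 16 conditions (2^4 and the 16-row table in 3.2; the 2 × 2 × 2 × 4 also printed there does not match that table); 2 people per condition and N = 32 (3.8); blocks of 16 (3.7.1); benchmark 80% (3.6.2). The plan states no SD, effect size or expected rates, so all rates below are assumptions.

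**1. The plan's own figure.** 16 × 2 = 32. It reproduces.

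**2. Groups by number of harder goals, k.** The conditions with k = 0, 1, 2, 3, 4 number 1, 4, 6, 4, 1. At two people each this gives 2, 8, 12, 8, 2 people. The end groups are simply conditions 1 and 16, with 2 people each, so a usable table collapses to 0-1, 2 and 3-4: 10, 12, 10. This assumes that both blocks of 16 are filled.

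**3. Assumed example, 8 points lost per harder goal.** Retention is 96, 88, 80, 72, 64% for k = 0 to 4.
- Pooled: (2×96 + 8×88 + 12×80 + 8×72 + 2×64)/32 = 2560/32 = 80%.
- 0-1 harder goals: (2×96 + 8×88)/10 = 89.6%.
- 3-4 harder goals: (8×72 + 2×64)/10 = 70.4%.
- Each main effect is 8 points (84% easier, 76% harder). Every interaction on the percentage-point scale is zero, because the losses add.

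In simulation, a little over half of such pilots retain 26 or more of 32 and meet the benchmark.

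**4. Milder example, 5 points per goal from 95%.** Pooled 85%; 91% with 0-1 and 79% with 3-4. The benchmark is met in about 81% of simulated pilots.

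**5. What the slope on k adds.** The sum of squares of k about its mean of 2 is 2×4 + 8×1 + 12×0 + 8×1 + 2×4 = 32.
- Slope SE = SD/√32 = 0.177 SD per harder goal.
- Main-effect SE = SD × √(1/16 + 1/16) = 0.354 SD.

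Code each goal as x = +1 (harder) or −1 (easier). Then k − 2 is half the sum of a person's four x values, the slope is Σ(k − 2)y/32, and a main effect is Σxy/16. Hence slope = (1/64) × (sum over the four goals of Σxy) = (sum of the four main effects)/4. The slope is exactly the average of the four main effects. Simulation confirms this with no difference.

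**6. Precision.** Near 80%, SD = √(0.8 × 0.2) = 0.40. The slope's 95% half-width is 1.96 × 0.40 × 0.177 = 0.139, or about ±14 points per goal. For one main effect it is 1.96 × 0.40 × 0.354 = 0.277, or about ±28 points. Exact 95% intervals are 64% to 93% for 26/32 and 44% to 97% for 8/10.

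**7. How often it would show the pattern in step 3** (200,000 simulated pilots). The slope has the right sign in 83% and one main effect in 64%; all four main effects have it together in 18%. The slope's 95% CI excludes zero in the harmful direction in only 18%. The 3-4 group looks no worse than the 0-1 group in 20%. With no effect at all and 80% throughout, the 3-4 group still looks at least 20 points worse in 20%.

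**The case against.** The strongest reply is that additive burden is what main effects measure, and 3.9 plans main effects. A reader might infer that the plan reads combined effects only through interactions, so that burden adding up across goals stays hidden. The documents do not support that. Section 3.9 names main effects together with interactions, and by step 5 the slope holds nothing that the four main effects do not. Its better sign rate comes from averaging, not from new information. What remains is that 3.9 attaches main effects to efficacy outcomes, not to these rows.

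A reader might also infer that combinations are to be judged on cells of two people. They are not. "the same number of participants (n=2) per condition" is a reason for the sample size, and sections 3.2 and 3.9 pool across conditions.

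Three further points have weight:
- The opening of section 3 promises to examine effects on goal attainment and self-monitoring engagement. For the three tracking rows the intention is therefore stated, and 3.9 merely fails to carry it through. For retention, survey completion and recommending the program there is no such statement.
- Section 2.5 places evaluation of unique and combined effects in the later powered trial. That holds for efficacy. Whether people stay in and complete the program under several harder goals is a feasibility question, and section 2.1 puts feasibility here.
- A count of harder goals treats four unlike manipulations as equal, while levels will be chosen goal by goal. This stands, and is why the count cannot replace the main effects.

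**Conclusion.** The point holds as a gap in the analysis text, not as a design flaw. Section 3.9 states no breakdown by assigned intensity for six whole-person primary results, although the pilot's question is about intensity. A pooled pass can coexist with a shortfall among people given 3-4 harder goals: about 70% against 90% under the assumed 8-point gradient, 79% against 91% under 5 points. Both gradients are illustrations, and the first was chosen to land on 80%. Nothing in the documents says that such a gradient exists.

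The remedy should not be oversold. With N = 32 it would usually point the right way under the larger gradient but would seldom establish harm, and it can look alarming by chance. It is worth doing because it uses groups already randomised and data already collected, and because stating the grouping beforehand prevents its being chosen after the results are seen.

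**What to change.** Add to 3.9:

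*For 10-week retention, 10-week survey completion, recommending the program, and tracking of weight, steps and diet, results will be shown overall against the benchmark and by easier versus harder level of each goal. An exploratory table will show the same rows by number of harder goals assigned (0-1, 2, 3-4; n = 10, 12, 10), with the least-squares slope per additional harder goal and its 95% CI. Yes/no rows will show counts, numbers assigned and observed, and exact 95% intervals; tracking rows will show means and SDs. In this balanced design the slope equals the average of the four main effects (SE 0.18 SD, against 0.35 SD for one main effect). It weights the four goals equally and is imprecise (about ±14 points per goal for a percentage near 80%). It accompanies the main effects and does not replace them.*

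The equality is exact for complete data on all 32. It holds for retention by assignment, and only approximately where responses are missing, as they may be for recommending the program.

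The cost is a short paragraph and one extra table, with no new data and no change to design or sample size. The one risk is over-reading small groups, which the exploratory label and the intervals are there to limit.

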3.1 Overview

All participants will receive a core intervention and either an easier or harder version of 4 goal domains: calorie goal, step goal, eating window goal, and Red Zone Food goal. The intervention will last 10 weeks, with remote assessments at baseline, 4 weeks, and 10 weeks. All procedures, including the intervention and assessment, will occur remotely.

3.2 Study Design

This optimization trial will use a 2^4 full factorial design (i.e., $2 \times 2 \times 2 \times 4$) to test easier vs. harder versions of 4 goals. As shown in the **Table**, for each goal domain, half of participants will be randomly assigned to receive the easier version while the other half will receive the harder version. In total, participants will be randomized to 1 of 16 experimental conditions. A factorial trial compares means across *combinations* of conditions in order to test main effects of components and their interactions. For example, the main effect of calorie goal intensity is the mean for the participants who receive the easier version of it (i.e., experimental conditions 1-8) versus the mean of those who receive the harder version of it (i.e., conditions 9-16).

| Experimental Condition | Core | Calorie Goal | Step Goal | Eating Window Goal | Red Zone Food Goal |
|------------------------|------|--------------|-----------|--------------------|--------------------|
| 1 A | Yes | Easier | Easier | Easier | Easier |
| 2 B | Yes | Easier | Easier | Easier | Harder |
| 3 C | Yes | Easier | Easier | Harder | Easier |
| 4 D | Yes | Easier | Easier | Harder | Harder |
| 5 E | Yes | Easier | Harder | Easier | Easier |
| 6 F | Yes | Easier | Harder | Easier | Harder |
| 7 G | Yes | Easier | Harder | Harder | Easier |
| 8 H | Yes | Easier | Harder | Harder | Harder |
| 9 I | Yes | Harder | Easier | Easier | Easier |
| 10 J | Yes | Harder | Easier | Easier | Harder |
| 11 K | Yes | Harder | Easier | Harder | Easier |
| 12 L | Yes | Harder | Easier | Harder | Harder |
| 13 M | Yes | Harder | Harder | Easier | Easier |
| 14 N | Yes | Harder | Harder | Easier | Harder |
| 15 O | Yes | Harder | Harder | Harder | Easier |
| 16 P | Yes | Harder | Harder | Harder | Harder |

3.3 Study Population

3.3.1 Recruitment

Participants will be recruited through several remote channels nationwide and in the San Francisco Bay Area: a) social media posts (Twitter and Facebook), b) research registries (ResearchMatch.org, a national registry of health research volunteers; ClinicalTrials.gov registry; the Stanford Diabetes Research Center's registry comprised of adults with pre-diabetes or type 2 diabetes, as well as healthy individuals); c) community advertisements (Nextdoor, Craigslist), and/or d) university-affiliated research websites. The target recruitment is 32 participants. Briefly, eligibility criteria

include: adults ≥ 18 years, body mass index (BMI) 25-45 kg/m², smartphone ownership, no recent weight loss ≥ 10 lbs., and no condition that contraindicates weight loss.

